Study Protocol and Statistical Analysis Plan for Research Project: "Design and Development of a Mobile App to Improve Adherence to Pre-exposure Prophylaxis in Men Who Have Sex with Men?" clinicaltrials.gov
#NCT04248790 December, 28, 2020

Study design: This study is an open label, single group assignment, interventional study, aiming to examine the preliminary effectiveness of the app in monitoring adherence to PrEP. The study expects to enroll participants since May, 2020 and follow-up for 4 months.

Participants:

Inclusion criteria:

- Male.
- Aged 20 or above.
- Resides in Taiwan and able to understand, read, and speak Mandarin Chinese.
- Remains HIV negative prior to and during the study period.
- The results of the laboratory tests are eligible to initiate PrEP.
- Currently taking PrEP or willing to initiate PrEP.
- Reports having 4 times or above anal sex with men in the past month.
- Owns an Android or Apple operating system (iOS) smartphone and willing to download the study app.
- Willing to wear the device we provided during the study period.

Exclusion criteria:

- With abnormal kidney function (creatinine clearance rate \leq 60 mL/minute).
- Currently on medication that might interact with PrEP, such as drugs contain lamivudine in the pre-PrEP assessment.

Sample size: above 30 participants and 70 participants at maximum. The sample size calculation is based on central limit theorem (CLT), which states that the distribution of sample means approximates a normal distribution as the sample size gets larger. CLT refers to that sample sizes equal to or greater than 30 are considered sufficient for the CLT to hold.

Interventions: The UPrEPU app is a self-monitoring tool to improve PrEP adherence regardless of the MSM user's choice of dosing regimen and lifestyle. All of participants will receive access to all the app capabilities. The app features include information on HIV testing locations, sex and PrEP diary and reminder of taking PrEP.

Data Collection:

Recruitment: Participants from two medical centers in two major cities of Taiwan. Potential study participants will be referred by physicians and case navigators from the clinics.

Screening: Their eligibility will be assessed by a screening tool available online. Screening questionnaire shown in Table 1. The participants' answers have to meet "Answers to enroll" in each question to enroll this study.

Table 1. Screening questionnaire

Questions	Options	Answers to enroll

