What is your gender	 Male  Female	Male
Are you able to understand, read, and speak Mandarin Chinese	 Yes  No	Yes
Are you living in Taiwan	 Yes  No	Yes
HIV status	 Positive  Negative	Negative
Do you assess the pre-PrEP assessment and eligible to use PrEP	 Yes  No	Yes
Birth Year	Open question	<=1999
Currently or willing to use PrEP	 Yes  No	Yes
Do you ever have anal intercourse with men	 Yes  No	Yes
How many episodes of anal intercourse with men in the past month	Open question	>=4
What is your cell phone brands and models	Open question	Only smart phone is available

Afterward, trained research assistants will inform those who are eligible about the purposes of the study and the information that will be collected in the study.

Individuals who express interest in this study will be required to provide signed informed consent. For those who do not consent to participate, the reasons for declining participation will be documented.

Baseline visit: Eligible participants will download the UPrEPU app on their phone and answer a baseline questionnaire in the app regarding sociodemographics, mental health scales, sexual behaviors, and PrEP use at the baseline visit at the study site.

Participants will also receive a wearable device that collects physiological sensor data. Participants will be encouraged to use all app components over the next four months and wear the wearable devices at all times.

Follow-up visit: Participants will be followed up monthly for the four months at the two medical centers where they were recruited. Each monthly visit will include rapid testing for HIV antigen and antibodies, measuring TDF/FTC concentration, and complete a follow-up questionnaire on their mental health scales, sexual behaviors, and PrEP use. Depression and anxiety will be assessed by Patient Health

Questionnaire-9 (PHQ-9) and General Anxiety Disorder-7 (GAD-7). We collect these two mental health indicators since studies have shown that mental health status may be associated with adherence to medications.

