Kidney function and sexually transmitted infections will be assessed at the end of follow-up. The system usability scale (SUS) for the UPrEPU app will be assessed during the first follow-up visit and at the end of the study. A face-to-face, semi-structured qualitative interview will be conducted at each visit to assess the feasibility of the app. It will focus on any technical challenges participants may have encountered, recommendations for app improvement, and their satisfaction and comfort in using this app. All interviews will take around 30 minutes and will be audio-recorded for transcription and analysis. Data collection Items and Schedule shown in Table 2.

Table 2. Data collection Items and Schedule

	Screening	Baseline	F-up -1	F-up -2	F-up -3	F-up -4
1. Eligibility/Interest	●					
2. Informed Consent	●					
3. Blood sample		●	●	●	●	●
A. Drug concentration ◎Can be collected either F-up-2, F-up-3, or F-up-4				◎	◎	◎
B. HIV test		●	●	●	●	●
C. Liver and kidney function		●				●
D. Syphilis screening		●				●
4. Installing UPrEPU app		●				
5. Set up smart device		●				
6. Receive data in smart device			●	●	●	●
7. Baseline questionnaire		●				

8. Follow-up questionnaire			●	●	●	●
9. SUS questionnaire			●			
10. APP feasibility interview			●	●	●	●
11. Incentive			\$20	\$20	\$20	\$20 OR \$53

Incentives: Participants will receive incentives for completing each follow-up visit and in-depth interview. This includes US \$20 cash for each follow-up visit and US \$33 cash for twice completing the in-depth interviews. Participants whose cumulative frequency of log-in and use of features reached 90% will receive an additional US \$33 at the end of the study.

Statistical analysis plan: Usability of the app will be measured by the System Usability Scale (SUS), a 10-item, 5-point Likert scale, which gives a global view of subjective assessment of usability [1]. A score above 50 out of 100 indicates acceptable [2]. The primary feasibility outcomes include frequency of app log-in, use of app components such as PrEP-taking and sexual behavior reports, and the length of time of the app use based on the app analytics. Descriptive statistics will be used and confidence intervals will be calculated to evaluate the primary feasibility outcomes. Secondary feasibility outcomes of this app will be analyzing data from qualitative interviews focusing on technical challenges and satisfaction of the app during the follow-up with thematic analysis methods.

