We will examine the app users' effectiveness of adherence monitoring for this app by comparing the pill-taking reports in the PrEP-taking diary component in the app with the Tenofovir (TDF) and Emtricitabine (FTC) drug concentration in dried blood spot (DBS) samples in the previous seven days before the follow-up day. We will use correlation analysis to examine the consistency between the drug concentration in the DBS samples and self-reported PrEP diary in the app. Higher correlation reflects higher effectiveness of adherence monitoring.

Reference

1. Brooke J, *SUS-A quick and dirty usability scale*. Usability evaluation in industry. Vol. 189. 1996. 4-7.

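### The monitoring aim is judged only by the size of a diary-to-drug-level correlation, which alone cannot give the direction of diary error or exclude systematic error

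*Combined protocol and SAP*

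**What the plan says.** Under Study design, the document describes a preliminary study: "This study is an open label, single group assignment, interventional study". Its aim is to "examine the preliminary effectiveness of the app in monitoring adherence to PrEP". The planned size is above 30 and at most 70.

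The last paragraph of the Statistical analysis plan compares diary pill reports with TDF and FTC concentration in DBS samples, over the seven days before the follow-up day. It names one analysis: "We will use correlation analysis to examine the consistency between the drug concentration in the DBS samples and self-reported PrEP diary in the app". It gives one reading of the result: "Higher correlation reflects higher effectiveness of adherence monitoring". It does not state the type of correlation, a threshold, a confidence interval for r, a conversion from concentration to expected pills, or any count of over- or under-reporting.

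Intervals are planned elsewhere: "Descriptive statistics will be used and confidence intervals will be calculated to evaluate the primary feasibility outcomes". Those outcomes concern app use. The usability scale and the interviews concern usability and feasibility. None of them measures whether the diary is accurate.

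The number of diary-DBS pairs per person is unclear. The Follow-up visit section says: "Each monthly visit will include rapid testing for HIV antigen and antibodies, measuring TDF/FTC concentration". The drug-concentration row of Table 2 says: "Can be collected either F-up-2, F-up-3, or F-up-4".

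**The concern.** The plan treats association as if it were consistency. A correlation shows whether people who log more pills tend to have higher drug levels. It does not show whether the number logged is right.

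A monitoring tool has to show whether users log pills they did not take or leave out pills they took. Under the plan's rule, a systematically wrong diary could be read as effective, and a correct diary in a uniformly adherent group could be read as ineffective. Direction has some relevance here because an extra payment depends on log-in and feature use reaching 90%. That is a possible motive to over-log, although the documents do not say that it has this effect.

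**Working it through.** **The plan's own figure.** There is none to reproduce. The plan sets no target or precision for r, and the sample size rests on a central-limit rule of thumb.

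**Step 1: algebra, with no assumptions about the data.** For diary X, level Y and b > 0:

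corr(a + bX, Y) = b·cov(X, Y) / [b·sd(X)·sd(Y)] = corr(X, Y).

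Any constant or proportional diary error therefore leaves r unchanged, at any sample size.

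**Step 2: simulation.** The inputs are assumptions, not figures from the documents:
- level = pills taken in 7 days × exp(N(0, SD)), with SD 0.3 (range 0.2 to 0.5);
- Pearson r, 400,000 draws per scenario;
- 80%-adherent daily users drawn as Binomial(7, 0.8).

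| True pills in 7 days | Diary | r at SD 0.3 | r at SD 0.2; 0.5 |
|---|---|---|---|
| Uniform 0–7 | Perfect | 0.87 | 0.94; 0.72 |
| Uniform 0–7 | Half of missed days logged as taken | 0.68 | 0.73; 0.56 |
| Uniform 0–7 | Half of taken days omitted | 0.68 | 0.73; 0.56 |
| Uniform 0–7 | +2, capped at 7 | 0.84 | 0.91; 0.69 |
| Daily, 80% adherent | Perfect | 0.52 | 0.68; 0.33 |
| Daily, 80% adherent | 2 pills short | 0.52 | 0.68; 0.33 |
| Daily, 80% adherent | +2, capped at 7 | 0.385 | 0.51; 0.25 |
| 90% at 7, 10% at 6 | Perfect | 0.14 | 0.21; 0.08 |

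**Step 3: what r misses.** Group both measures at 1.5, 3.5 and 5.5 pill-equivalents (assumed cuts, SD 0.3). Call a pair over-reported if the diary group is above the level group, and under-reported if it is below.
- The two diaries with r = 0.68 have over-/under-reported shares of 64%/3% and 2%/57%.
- With true pills 0–7, adding 2 capped at 7 raises the over-reported share from 15% to 71%, while r goes only from 0.87 to 0.84. Spearman goes from 0.918 to 0.912.
- In 80%-adherent users, the diary 2 pills short raises the under-reported share from 13% to 74%, with r still 0.52.

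**Step 4: precision.** The Fisher interval is tanh[atanh(r) ± 1.96/√(n − 3)]. For r = 0.84, atanh(r) = 1.221.
- n = 31: 1.221 ± 0.370 gives 0.69 to 0.92.
- n = 70: 1.221 ± 0.239 gives 0.75 to 0.90.

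Both intervals contain 0.87, the value for the perfect diary. In repeated samples with true pills 0–7, r ranks the perfect diary above the +2 diary in 65% of pairs at n = 31 and 73% at n = 70.

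**Step 5: the same test applied to the remedy.** Take a perfect diary at SD 0.3 and a calibration that reads 20% low (assumed). The over-reported share rises from 15% to 32% with true pills 0–7, and from 26% to 51% in 80%-adherent users. At 30% low the shares are 43% and 67%. In every case r is unchanged.

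**The case against.** A reader might infer that correlation cannot show whether the diary is wrong at all. That goes too far. Random mis-logging lowers r from 0.87 to 0.68 in the wide-range scenario. In an assumed 50/50 mix of high- and low-frequency users at n = 31, r ranks a perfect diary above an uninformative one in 96% of sample pairs, against 88% for the over-reported share.

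A reader might also infer that over-reporting limited by the 7-pill ceiling always leaves r almost unchanged. It does so across a wide dose range. In 80%-adherent daily users, r falls from 0.52 to 0.385, about a quarter. In that population +2 and −2 give different r, so equal r for opposite errors is possible but not general. The documents do not give the adherence distribution.

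The strongest defence of r is its indifference to scale. Diary counts and concentrations are in different units, and the documents give no calibration. Step 5 shows that a biased calibration can make a perfect diary look over-logged while r is unaffected. The plan also names two analytes, and a cross-table needs a rule for which one defines the level group.

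Finally, the study calls itself preliminary, no decision depends on r, and the rule is a relative reading that does not claim absolute accuracy.

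These points lower the weight and make the cross-table conditional. They do not repair the rule: no other analysis covers direction or systematic error, and the algebra in step 1 holds whatever the stage of the study.

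**Conclusion.** The point holds in this form: r alone cannot identify the direction of diary error, a high r does not exclude systematic over- or under-reporting, and a low r can occur with a correct diary when adherence is uniformly high. The documents do not support the stronger reading that r carries no information about diary error, nor the view that percentages should replace r.

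The invariance to constant and proportional error is exact. The r values and shares rest on proportional levels, the assumed noise, the assumed dose distributions and, for the shares, the assumed cuts.

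The weight is minor to moderate. It affects how the stated aim can be interpreted, but leaves the feasibility and usability outcomes untouched.

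**What to change.** 1. Replace the interpretive sentence with: *Correlation describes association between diary and drug level; it does not by itself show that the diary is accurate.*
2. Report r with its 95% CI.
3. If a named assay calibration is available, fix in advance the analyte (TDF or FTC, and what is reported if they disagree) and the groups. Beside r, report a cross-table of 7-day diary count group against drug-level group, with the over-reported and under-reported percentages and their 95% CIs.
4. If no calibration is available, state that the direction of error cannot be assessed.
5. Reconcile the Follow-up visit section with Table 2 on how often drug level is measured. Use one diary-DBS pair per participant, or person-clustered CIs if there are more.

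**Cost.** One reworded sentence, one interval and, conditionally, one table on data already planned, plus a calibration source that the documents do not supply.

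**Downsides to state.**
- The percentages depend on the cuts, the assay noise and the adherence range. At SD 0.3, noise alone labels a perfect diary over-reported in 10% to 26% of pairs across the scenarios examined.
- Calibration bias can create false over-reporting, as in step 5.
- Precision is limited: the Wilson 95% CI is 9% to 36% for 6/31 and 12% to 31% for 14/70.

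The SAP should therefore say that the percentages complement r and do not replace it.
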